7.4.1.2 Secondary Analysis

The same analysis of the primary variable as described in Section 7.4.1.1 will be conducted using the PPS. A sensitivity analysis will be conducted to impute the missing data.

7.4.1.3 Subgroup Analysis

Subgroup analyses for sex, age, and other categories may be explored.

7.4.2 Analysis of Secondary Variables

For secondary efficacy endpoints, binary variables such as Percentage of subjects achieving ACR50 response at Week 12/ET, Percentage of subjects achieving ACR70 response at Week 12/ET will be analyzed using Fisher's exact test, and continuous variables, such as Change from baseline/Day 1 to Week 12/ET in DAS28-CRP and DAS28-ESR scores, will be analyzed using ANCOVA with treatment group as factor and baseline as covariate. Each ASP015K group will be compared with placebo group and multiplicity for the secondary efficacy variables will not be adjusted.

- CONFIDENTIAL -

7.5 Analysis of Safety

The following analyses will be performed in SAF. Unless otherwise noted, analyses will be performed in the treatment groups at allocation (ASP015K 100 mg group, ASP015K 150 mg group, placebo group) and, when necessary, in the treatment groups after placebo was switched to active treatment (ASP015K 100 mg group, ASP015K 150 mg group, placebo–ASP015 100 mg group at Week 12, placebo–ASP015K 150 mg group at Week 12, placebo–ASP015K 100 mg group at Week 28, and placebo–ASP015K 150 mg group at Week 28).

7.5.1 Adverse Events

AEs will be coded using the Medical Dictionary for Regulatory Activities (MedDRA). The incidence of AEs, SAEs, AEs leading to discontinuation, and AEs whose relationship to the study drugs could not be ruled out will be summarized by system organ class and preferred term, as well as the treatment group. The incidence of AEs by severity will also be summarized.

7.5.2 Laboratory Assessments

Descriptive statistics will be used to summarize clinical laboratory measurements and the change from baseline if quantitative, by time point. The frequency of each discrete value will be summarized by time point.

7.5.3 Vital Signs

Descriptive statistics will be used to summarize vital sign measurements and the change from baseline by time point.

7.5.4 12-lead ECG

The frequency of each category of 12-lead ECG results will be summarized by time point.

7.5.5 QT Assessment

- Descriptive statistics will be used to summarize QT assessment (including QTc assessment) measurements and the change from baseline.
- The frequency of each category of QT assessment (including QTc assessment) will be summarized by time point.

In addition, the relationship between quantity of QT change and concentration of ASP015K may be explored.

7.5.6 Body Weight

Descriptive statistics will be used to summarize measurements by time point.

7.6 Analysis of Pharmacokinetics

A detailed elaboration of the PK analysis will be included in a separate PK analysis plan. The trough plasma concentrations of ASP015K will be summarized by treatment group and visit. Exploratory population PK analysis may be performed by pooling the results obtained so far.

- CONFIDENTIAL -

7.7 Other Analyses

7.7.1 Analysis of Pharmacodynamics

Analysis will be performed in PDAS. Descriptive statistics will be used to summarize PD measurements and the change from baseline by time point.

7.7.2 Analysis of Pharmacogenomics

At present, the content of analysis as part of pharmacogenomic research has not been determined yet. The relationship between the results from genetic analyses and study data (clinical information such as pharmacological activity, toxicity and PK) may be explored in the future. The sponsor can initiate such research once a specific methodology is established. Prior to research, the sponsor will prepare a research plan (including procedures and timing of document disposal) and have appropriateness of conduct of the research reviewed and approved by the sponsor's ethics review committee from ethical and scientific viewpoints.

7.8 Interim Analysis (and Early Discontinuation of the Clinical Study)

Not applicable. Review of safety data and safety evaluation will be completed by an independent DSMB [see Section 10.1 Independent Data and Safety Monitoring Board (DSMB)] during the study in accordance with separate SOP.

7.9 Handling of Missing Data, Outliers, Visit Windows, and Other Information

Final judgments on handling of missing data, outliers, visit windows, and other information will be made at the Case Review Meeting based on the opinions and advice from a medical expert and/or statistical advisor prior to treatment code breaking and included in the SAP.

The acceptable time ranges of the efficacy and safety examinations, observations, etc. from the date of initial study treatment (Day 1) are defined as follows. If there are multiple data available over the same period of time, the data obtained on the date closest to the reference date will be utilized; the later date will be applied if the number of days from the reference date is equal. Subjects who have no evaluable post-dose data on ACR20, ACR50, and ACR70 response rates will be counted as non-responders and included in the analysis at the end of Week 12 (Week 12 or at early termination before Week 12).

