5.4.4.1 CPK Monitoring

If a CPK elevation is observed after administration of the study drug begins, CPK will be monitored as follows.

- If laboratory testing reveals $CPK > 3 \times ULN$, and the subject is asymptomatic, retest CPK preferably within 1 week of previous blood sampling to confirm it. Subsequently, retest CPK weekly (from the date of the initial CPK elevation) until $CPK \leq 3 \times ULN$ or is stable according to the judgment of the investigator/sub-investigator. If the retest cannot be performed within 1 week of blood sampling, which marks the starting point of CPK monitoring, suspension or interruption of the study drug should be considered until the retest results are obtained.
- In subjects whose baseline CPK is already $> 3 \times ULN$, if laboratory testing reveals $CPK > 2 \times$ baseline, and the subject is asymptomatic, retest CPK preferably within 1 week of previous blood sampling to confirm it. Subsequently, retest CPK weekly (from the date of CPK elevation to $> 2 \times$ baseline) until $CPK \leq 2 \times$ baseline, or is stable in the judgment of the investigator/sub-investigator. If the retest cannot be performed within 1 week of blood sampling, which marks the starting point of CPK monitoring, suspension or interruption of the study drug should be considered until the retest results are obtained.
- If CPK is $> 10 \times ULN$ at any time, treatment will be immediately suspended or interrupted (see Section 3.4 Discontinuation Criteria for Individual Subjects), and retest CPK.
- If there is a symptomatic CPK elevation (CPK elevation $> 1.5 \times ULN$ accompanied by severe and unusual episodes of myalgia, muscular weakness, or muscle twitching), as reported by the investigator/sub-investigator, treatment will be immediately discontinued (see Section 3.4 Discontinuation Criteria for Individual Subjects).

In the retest for CPK monitoring, the following tests will be performed in addition to CPK measurements. The content of the subject questionnaire will be entered in the eCRF.

- Laboratory tests
(Measurement parameters: CK-MB, troponin T, aldolase)
- A targeted physical examination* and subject questionnaire to assess muscle strength and pain
*: As part of the targeted physical examination, urinalysis (blood and microscopy) will be performed.

- CONFIDENTIAL -

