5.4.4.2 Hepatic Function Abnormal

If laboratory testing for a subject enrolled in the study and receiving the study drug reveals an increase in serum aminotransferase (ALT, AST) $> 3 \times \text{ULN}$ or TBL $> 2 \times \text{ULN}$, at least 4 parameters (ALT, AST, ALP, and TBL) of the usual hepatic function test parameters should be retested. The retest should be performed between 48 hours and 72 hours after notification of the test results.

For additional information on monitoring and the assessment of the hepatic function test, see Appendix 4 “Liver Safety Monitoring and Assessment.”

If laboratory testing for a subject enrolled in the study receiving the study drug reveals an increase in serum aminotransferase (ALT, AST) $> 3 \times \text{ULN}$ and TBL $> 2 \times \text{ULN}$, the investigator will determine whether it is an SAE. Even if the abnormality is not considered an SAE by the investigator/sub-investigator, it will be reported to the sponsor or CRO in writing as in the case of SAEs.

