### 7.5.2.1 Liver Abnormalities

The following potentially clinically significant criteria in liver function tests for Alkaline Phosphatase (ALP), Alanine Transaminase (ALT), total bilirubin, Aspartate Transaminase (AST) and their combination are defined. The subject's highest value during the investigational period will be used.

Parameter	Criteria
ALT	> 3xULN
	> 5xULN
	> 10xULN
	> 20xULN
AST	> 3xULN
	> 5xULN
	> 10xULN
	> 20xULN
ALT or AST	> 3xULN
	> 8xULN
Total Bilirubin	> 2xULN
ALP	> 1.5xULN

ALT and/or AST OR Total Bilirubin (\*) (ALT and/or AST > 3xULN) or  
total bilirubin > 2xULN

ALT and/or AST AND Total Bilirubin (\*) (ALT and/or AST > 3xULN) and total bilirubin  
> 2xULN

(\*) Combination of values measured within same sample

The number and percentage of subjects with potentially clinically significant values in liver function tests during the investigational period will be presented by treatment group.

Additionally, confirmed liver abnormalities will be characterized as moderate and marked, as follow:

Moderate: ALT or AST > 3×ULN OR Total Bilirubin > 2×ULN.

Marked: ALT or AST > 3×ULN AND Total Bilirubin > 2×ULN.

Number and percentage of subjects in each category at each scheduled visit will be summarized. These combinations of elevated values are based on measured value within the same sample.

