#### **7.11.3 Visit Windows**

The acceptable time ranges of the efficacy and safety examinations, observations, etc. from the date of initial study treatment (Day 1) are defined as follows. If there are multiple data available over the same period of time, the data obtained on the date closest to the reference date will be utilized; the later date will be applied if the number of days from the reference date is equal. Subjects who have no evaluable post-dose data on ACR20, ACR50, and ACR70 response rates will be counted as non-responders and included in the analysis at the end of Week 12 (Week 12 or at early termination before Week 12).

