**Table10. Visit Window for Vital signs, laboratory test (hematology, biochemistry, urinalysis)**

Time points defined in analysis	Reference date*	Acceptable time range
Screening	Day -28 to Day -1	Day -28 to Day -1
Baseline	Day 1	Day 1
Week 4 to Week 48**	Day $7 \times x + 1$	Day $(7 \times x - 6)$ to Day $(7 \times x + 8)$ and before drug administration on the visit day
Week 52	Day 365	Day 358 to Day 372
Minimum on Treatment up to Week 12***		Minimum value at allowance Range (Day 2 to Day 92) before first dose of Week 12 study drug
Maximum on Treatment up to Week 12***		Maximum value at allowance Range (Day 2 to Day 92) before first dose of Week 12 study drug
Minimum on Treatment***		Minimum value during Entire Period (No limitation for period)
Maximum on Treatment***		Maximum value during Entire Period (No limitation for period)
Week 12/ET (Week 12 or at early termination before Week 12)	Day 85	Day 2 to Day 92
Week 28/ET (Week 28 or at early termination before Week 28)	Day 197	Day 2 to Day 204
EOT (Week 52 or at early termination)	Day 365	Day 2 to Day 372

\*: Day 1 represents the first day of study treatment. The day before is expressed as Day -1.

\*\* : Represents the reference date and acceptable time range for Week x.

\*\*\*: Applied to laboratory test only.

(2) Laboratory test (fasting lipid profile test)

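### The closest-date rule does not separate scheduled samples from triggered CPK and liver retests, so by-visit and Week 12/ET laboratory summaries tend to be pulled toward normal

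*Protocol*

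**What the plan says.** Protocol 7.9 settles competition within a window by distance: "the data obtained on the date closest to the reference date will be utilized; the later date will be applied" when two dates are equally far away. SAP 7.11.3 repeats this: "If there are multiple data available over the same period of time, the data obtained on the date closest to the reference date will be" the one that counts. SAP 7.11.5 applies the same closest-date choice to safety data at Week 12/ET and Week 28/ET. None of these sections distinguishes a scheduled sample from a retest or an unscheduled one.

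For hematology, biochemistry and urinalysis, SAP Table 10 sets each by-visit window at 7 days either side of the reference day, with the condition "and before drug administration on the visit day". The Week 12/ET row runs from Day 2 to Day 92 and has no such condition.

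The protocol orders repeat samples after abnormal results. For asymptomatic CPK above 3 × ULN, Protocol 5.4.4.1 says to "retest CPK preferably within 1 week of previous blood sampling to confirm it", then weekly. For ALT or AST above 3 × ULN, or bilirubin above 2 × ULN, Protocol 5.4.4.2 says "The retest should be performed between 48 hours and 72 hours after notification of the test results".

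Several outputs are built on one value per visit: actual values and changes at each visit, the shifts to Week 12/ET in SAP Table 18, and the moderate/marked liver table in SAP 7.5.2.1 ("Number and percentage of subjects in each category at each scheduled visit will be summarized").

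**The concern.** A triggered retest usually falls in the same window as the value that prompted it. Being later, it gains on the reference day whenever the scheduled visit was early. The rule then drops the planned observation and keeps a follow-up that exists because the planned one was high. Follow-up of a value selected for being high will on average be lower. By-visit laboratory summaries could therefore understate CPK and transaminase elevations, in a trial where CPK is a known signal for the drug.

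**Working it through.** **Inputs.** The window is Day 7x−6 to Day 7x+8 around Day 7x+1 (Protocol 7.9.2, SAP Table 10). For Week 12 the formula gives Day 78 to Day 92 around Day 85, which matches the Week 12 rows tabulated for lipids and body weight. The CPK retest lag is up to 7 days. The liver retest lag is 2 to 3 days after notification. The documents do not give the time from sampling to notification; I assume 1 to 2 days, so 3 to 5 days in all.

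**Condition.** Let o be the scheduled visit's offset from the reference day (−7 to +7) and g the retest lag. The retest is chosen if |o+g| ≤ 7 and |o+g| ≤ |o|, since a tie goes to the later date. This requires o < 0 and −o ≥ g/2. The visit must be early by at least 4 days when g = 7, 2 days when g = 3 or 4, and 3 days when g = 5. A visit on time or late always keeps the triggering value.

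**Examples.**
- Week 8 (Day 57): visit Day 52, retest Day 59. Distances 5 and 2; the retest is used.
- Week 8: visit Day 57, retest Day 64. Distances 0 and 7; the trigger is kept.
- Week 4 (Day 29): visit Day 26, retest Day 33. Distances 3 and 4; the trigger is kept.
- Week 4: visit Day 27, retest Day 31. Distances 2 and 2; the later value, the retest, is used.
- Week 4: visit Day 32, retest Day 39. The retest is outside the window (Day 22 to Day 36); the trigger is kept.

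**Share of triggering values replaced.** This is the share of visit offsets that meet the condition. The offset distributions are assumptions. The normal ones give each day o the weight Φ((o+0.5)/SD) − Φ((o−0.5)/SD), rescaled over −7 to +7.

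| Retest lag | Uniform ±7 | Normal, SD 3 | Normal, SD 2 | Uniform ±3 |
|---|---|---|---|---|
| 3 or 4 days | 6/15 = 40% | 31% | 23% | 2/7 = 29% |
| 5 days | 5/15 = 33% | 20% | 11% | 1/7 = 14% |
| 7 days | 4/15 = 27% | 12% | 4% | 0/7 = 0% |

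For example, SD 2 at 5 days sums offsets −7 to −3: Φ(−1.25) − Φ(−3.75) ≈ 0.106.

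**Scale.** In the Phase IIb study (Protocol 1.3), CPK increase was reported as an adverse event in 12.1% on 150 mg, 1.8% on 100 mg and none on placebo. Taken to 170 subjects, 0.121 × 170 ≈ 21 on 150 mg and 0.018 × 170 ≈ 3 on 100 mg. At 0% to 27% replacement, that is 0 to about 5 subjects on 150 mg (20.6 × 4/15 = 5.5) and at most about 1 on 100 mg. An adverse event is not the same as CPK above 3 × ULN, so this gives scale only.

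**Placebo switchers.** SAP 7.11.5 limits subjects who switch from placebo at Week 12 to observations before their first active dose. With a Week 12 visit on Day 80 and a retest on Day 87, a switcher keeps Day 80 for Week 12/ET, while a subject randomized to ASP015K gets Day 87.

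**Outputs that keep the peak.** SAP 7.5.2 plans shifts to highest and lowest values, toxicity grade to the worst value, and reference-range counts on highest or lowest values. SAP 7.5.2.1 uses each subject's highest liver values, and Table 10 defines a maximum over the entire period. SAP Table 18, however, lists the toxicity-grade shift as running to Week 12/ET and the reference-range table as by visit. Programmed that way, both would fall under the closest-date rule.

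**The case against.** The best defence is that peak toxicity is protected elsewhere. The highest-value and worst-value analyses and adverse event reporting keep the triggering value, and what remains is descriptive output without hypothesis tests. This largely stands and is the main reason for the modest rating. It is weakened only by the mismatch with Table 18.

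A second defence is that Protocol 7.9 leaves final data handling to the Case Review Meeting, to be written into the SAP. The final SAP, version 1.00, adds no exception.

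Third, some retests cannot compete. After the end of treatment, samples more than 2 days past the last dose are excluded, and the pre-dose condition may exclude others from by-visit cells. At Week 12/ET, retests from Week 4 or Week 8 lose to an available Week 12 sample. All of this is correct and lowers the rates.

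Stronger readings are tempting, but the documents do not support them:
- *That retests are often taken off drug.* Only at CPK above 10 × ULN does Protocol 5.4.4.1 say that, "at any time, treatment will be immediately suspended or interrupted". For asymptomatic values above 3 × ULN, "suspension or interruption of the study drug should be considered until the retest results are obtained" applies only when the retest cannot be done within a week. No liver test is on the suspension list in Protocol 3.4.1.1, and Appendix 4 asks only that discontinuation be considered.
- *That replacement runs in one direction only.* Protocol 5.4.4 also allows extra samples at the investigator's judgement and for defective specimens, and a retest can exceed its trigger. Only a net tendency toward normal can be claimed.
- *That the loss clearly falls on both active arms.* The Phase IIb CPK signal was at 150 mg, and Protocol 1.3 lists no transaminase rise against placebo.
- *That the moderate/marked liver table should take the worst value in the window.* SAP 7.5.2.1 and Protocol Appendix 4 define those categories on confirmed abnormalities. A value that normalises on retest may properly be left out.

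**Conclusion.** The point holds for by-visit and Week 12/ET laboratory summaries. As written, the rule lets a triggered retest displace its own trigger after an early visit, and the net effect is toward normal. Across the assumed offset patterns, about 4% to 27% of triggering CPK values would be replaced at a 7-day lag, and none if visits keep within 3 days of target. At 3 to 5 days the range is about 11% to 40%, which also applies to CPK retests done sooner than a week. These figures rest on assumed visit offsets and, for liver tests, an assumed notification delay. They do not allow for samples excluded by the pre-dose condition or the 2-day cut-off, and the documents do not allow the actual bias to be calculated. The efficacy analyses do not depend on these laboratory summaries. Importance is minor to moderate.

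**What to change.** In Protocol 7.9 and SAP 7.11.3 and 7.11.5, state for safety laboratory variables that:
- the by-visit and Week 12/ET value is the scheduled-visit sample, or the early-termination sample where that applies;
- a retest or unscheduled sample is used only if the scheduled sample is missing or unusable;
- all samples, retests included, enter the highest, lowest and worst-value analyses.

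Reconcile SAP Table 18 with SAP 7.5.2 so that the toxicity-grade shift uses the worst value and the reference-range counts use the highest or lowest value, or list both forms explicitly. Keep the confirmed definition for the moderate/marked liver table, and keep the closest-date rule for efficacy.

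The cost is a few sentences and a flag for scheduled versus unscheduled samples. By-visit abnormality counts may look slightly less favourable. No clinical procedure changes.

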7.9.1 Handling of Schedule of Assessments of Efficacy Variables

For data after the end of study treatment, data obtained within + 2 days after the last dose is taken will be included in analysis.

- CONFIDENTIAL -

(1) TJC (68 joints)/SJC (66 joints), laboratory test (CRP)

Time points defined in analysis	Reference date*	Acceptable time range
Screening**	Day -28 to Day -1	Day -28 to Day -1
Baseline	Day 1	Day 1
Week 4 to Week 48***	Day $7 \times x + 1$	Day $(7 \times x - 6)$ to Day $(7 \times x + 8)$ and before drug administration on the visit day
Week 52	Day 365	Day 358 to Day 372
End of Week 12 (Week 12 or at early termination before Week 12)	Day 85	Day 2 to Day 92
End of Week 28 (Week 28 or at early termination before Week 28)	Day 197	Day 2 to Day 204
End of treatment (Week 52 or at early termination)	Day 365	Day 2 to Day 372

*: Day 1 represents the first day of study treatment. The day before is expressed as Day -1.

**: PGA, SGA, subject's assessment of pain, CRP, and ESR are not applicable.

***: Represents the reference date and acceptable time range for Week x.

(2) Hand and foot radiography

Time points defined in analysis	Reference date*	Acceptable time range
Baseline	Day 1	Day 1 to Day 30
Week 28	Day 197	Day 160 to Day 234
Week 52	Day 365	Day 328 to Day 402
End of Week 28 (Week 28 or at early termination before Week 28)	Day 197	Day 48 to Day 234
End of treatment (Week 52 or at early termination)	Day 365	Day 48 to Day 402

*: Day 1 represents the first day of study treatment. The day before is expressed as Day -1.

(3) PGA and SGA (VAS), subject's assessment of pain (VAS), HAQ-DI, laboratory test (ESR)

Time points defined in analysis	Reference date*	Acceptable time range
Baseline	Day 1	Day 1
Week 4 to Week 48**	Day $7 \times x + 1$	Day $(7 \times x - 6)$ to Day $(7 \times x + 8)$ and before drug administration on the visit day
Week 52	Day 365	Day 358 to Day 372
End of Week 12 (Week 12 or at early termination before Week 12)	Day 85	Day 2 to Day 92
End of Week 28 (Week 28 or at early termination before Week 28)	Day 197	Day 2 to Day 204
End of treatment (Week 52 or at early termination)	Day 365	Day 2 to Day 372

*: Day 1 represents the first day of study treatment. The day before is expressed as Day -1.

**: Represents the reference date and acceptable time range for Week x.

- CONFIDENTIAL -

(4) SF-36 v2[®], WPAI

Time points defined in analysis	Reference date*	Acceptable time range
Baseline	Day 1	Day 1
Week 4 to Week 28**	Day $7 \times x + 1$	Day $(7 \times x - 6)$ to Day $(7 \times x + 8)$ and before drug administration on the visit day
Week 52	Day 365	Day 358 to Day 372
End of Week 12 (Week 12 or at early termination before Week 12)	Day 85	Day 2 to Day 92
End of Week 28 (Week 28 or at early termination before Week 28)	Day 197	Day 2 to Day 204
End of treatment (Week 52 or at early termination)	Day 365	Day 2 to Day 372

*: Day 1 represents the first day of study treatment. The day before is expressed as Day -1.

**: Represents the reference date and acceptable time range for Week x.

